The reduction and prevention of overweight and obesity in childhood represent today, one of the main missions of public health globally, both for short-term and long-term implications. Indeed, pediatric-onset obesity predisposes to an increased chance of obesity in adulthood and an early development of related diseases, including hypertension, Diabetes Mellitus, and insulin resistance (3,4). Today, the main treatment of obesity consists of substantial lifestyle modification (diet, physical activity, sedentariness) to achieve a permanent change in habits by involving the entire household [Level of evidence I, strength of recommendation A] (5). The Mediterranean Diet (DM) is one of the most effective tools for the prevention and treatment of obesity for the pediatric population. Obesity and overweight conditions in children and adolescents are established through the use of IOTF growth curves. Specifically, a state of overweight is defined from the 75th percentile and a state of obesity from the 95th percentile. (6)

Recently, the importance of bioimpedance analysis (BIA) in clinical routine has been evaluated, as it allows an estimate of body composition that would not otherwise be provided by growth curves and Body Mass Index (BMI) calculations.

In fact, BIA makes it possible to conduct both quantitative and qualitative analysis of body composition by assessing lean mass, fat mass, and body water percentage (intracellular and extracellular) in a noninvasive and inexpensive manner. In addition, through BIA the phase angle (PA) is assessed, which allows a more precise analysis of an individual's nutritional and hydration status by defining any conditions of malnutrition and/or dehydration (7). However, there are no studies conducted in pediatric settings about modulation of body composition in the literature.

Therefore, with our study we aim to investigate possible clinical and body composition changes in children and adolescents with overweight and obesity with the ultimate goal of reducing related cardio-metabolic risk factors.

PURPOSE OF THE STUDY

The aim of the study is to evaluate the effect of administering a normo/hypocaloric Mediterranean diet regimen on body composition in pediatric children, after 3 and 6 months from the start of the diet. Specifically, we want to evaluate the body composition of children and adolescents with overweight and obesity with respect to adherence to a dietary regimen, according to clinical practice. In particular, we want to evaluate the effect of administration of a normo/hypocaloric Mediterranean diet regimen on pediatric body composition.

MATERIALS AND METHODS

All children and adolescents who come to the SCDU of Pediatrics, Outpatient Endocrinology and Auxology Department of the Maggiore della Carità Hospital in Novara for first visit or checkup for excess weight between January 1, 2024, and May 30, 2024, of both sexes who satisfy the following inclusion criteria will be included in the study:

Inclusion criteria:

1. Ages between 6 and 17 years old;
2. BMI compatible with obesity or overweight according to IOTF criteria (6)
3. Signing of informed consent by parents/legal guardians.

Exclusion criteria:

1. Ages under 6 or over 18 years old
2. Previous diagnosis of type 2 diabetes mellitus already placed on dietary or drug therapy
3. Subjects already placed on a dieto-therapeutic regimen
4. Obesity secondary to diseases: genetic (Prader Willi syndrome, Down syndrome); metabolic and endocrine (Cushing's syndrome, hypothyroidism)

Informed Consent

After reading the study information sheet, patients will be enrolled only after signing the informed consent form by both parents or legal representative and recruited minor subjects (see patient and parent/legal guardian information sheets attached to the protocol).

Body composition measurement and dietary pattern definition

At enrollment (V1), included subjects will undergo a clinical examination as per normal practice, in which a bioimpedensiometric analysis for body composition assessment is planned. Impedenziometric analysis will be performed using a TANITA MC-780MA scale.

Following the bioimpedensiometric analysis and clinical examination, a dietary pattern based on the Mediterranean Diet will be delivered. The composition of the diet will be distributed as follows: 55-60% carbohydrates (45-50% complex carbohydrates and no more than 10% simple sugars), 25-30% lipids and 15% protein. It will be studied according to the LARN guidelines (Italian Society of Human Nutrition, 2014).

Follow-up

Patients will be evaluated at the time of enrollment (V1), after 3 months (V3) and after 6 months (V6) as per clinical practice.

At the recruitment visit (V1), the following demographic and medical history data of the patient and family will be collected:

sex, gender, age (years), ethnicity, weight and length at birth, type and duration of breastfeeding, parents' age (years), family history of previous diseases (Arterial Hypertension, Dyslipidemia, Hepatic Steatosis, Diabetes (specify whether type I or II and oral or insulin therapy) and cardiovascular disease, parents' smoking habit, presence of maternal gestational diabetes), socioeconomic level of the household.

The following assessments will be made at all times (V1,V3,V6):

1. Anthropometric measurements

- Height
- Weight
- BMI and BMI SDS
- Growth percentile according to Cacciari curves (8)
- Waist-to-hip circumference, waist-to-height ratio
- Bioimpedance analysis
- PA and heart rate

- Tanner Stadium (9)

2. Eating habits and anamnestic characteristics

- Semi-quantitative food frequency questionnaire (24h recall)
- KIDMED Mediterranean diet adherence questionnaire (10)
- IPAQ-A Physical Activity Questionnaire

Biochemical assessments will also be performed at the beginning and end of the protocol (V1 and V6), according to normal clinical practice (baseline hematochemical tests and/or OGTT). The tests will be performed at the clinical biochemistry laboratory of the AOU “Maggiore della Carità” in Novara.

During the biochemical evaluations, two serum and two plasma samples will be taken for Asprosine, Irisin, and Ghrelin dosage to search for new markers related to obesity and its complications. The analyses will be carried out at the Laboratory of Biochemistry at Eastern Piedmont University.

The determination of clinical parameters will be performed locally at the Pediatric Auxology and Endocrinology outpatient clinic of the Pediatric Clinic of the Maggiore della Carità Hospital in Novara, while the BIA examination will be performed at the Endocrinology outpatient clinic of the Maggiore della Carità Hospital in Novara.

EXPECTED RESULTS

A change in body mass index is expected, based on the BMI z-score and an improvement in body composition 6 months after the first visit and then the implementation of the dietary pattern. In addition, an improvement in metabolic parameters (insulin resistance, glycemic intolerance, dyslipidemia, hepatic steatosis) is expected.

DATA COLLECTION AND ANALYSIS

Data will be collected by the Principal Investigator, [name], at the outpatient clinic of Pediatric Endocrinology and Auxology at the AOU “Maggiore della Carità” in Novara and will be collected on an Excel file protected by username and password; each patient will be registered and identified by a code in order to ensure anonymity. Statistical analysis will be conducted by a Researcher from the University of Eastern Piedmont.

Calculation of sample size

Assuming a power of 80%, a first-type error of 0.05, a mean BMI z-score at V1 of 2.81, a corresponding standard deviation of 0.9 (12) a correlation between the measurements at V6 and V1 of 0.5, 70 children will be enough to be able to observe a change in BMI z-score of 0.3.

STATISTICAL ANALYSIS

Descriptive statistics will be used to summarize demographic and anamnestic characteristics, anthropometric measures, and adherence to the Mediterranean diet and physical activity at V1.

Specifically, for numeric variables the mean and standard deviation or median and interquartile range will be reported if not distributed according to a Gaussian distribution in accordance with the Shapiro-Wilks test while categorical variables will be reported as absolute and percentage frequencies. T tests for paired data will initially be used to assess the presence of variation in anthropometric measures between V6 and V1. Next, linear mixed-effects models will be used to assess the effect of Mediterranean diet adherence and time on anthropometric measures, adjusting for anthropometric measures at V1 and demographic and clinical characteristics at baseline. A random intercept will be included in the models to account for correlation of within-patient measures. The stepwise method will be used for the selection of variables to be included in the multivariable model.

All tests will be two-tailed, and the first-type error will be set at 0.05. The analyses will be performed with SAS version 9.4 (SAS Institute, Cary, NC, USA).

ETHICAL ASPECTS AND GOOD CLINICAL PRACTICE

All essential clinical records will be retained to demonstrate the validity of the study and the integrity of the data collected.

The study is designed and will be conducted according to the international and national ethical standards on biomedical research with human beings, specifically:

- *Ethical principles for medical research involving human subjects* (Declaration of Helsinki - World Medical Association, current version);
- European Union *Standards of Good Clinical Practice* (ICH/GCP);
- *Convention on Human Rights and Biomedicine* (Oviedo Convention of 04/04/1997);
- Italian codes of ethics for health professions and specific current national regulations on clinical trials.

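### The aim is worded as a diet effect, but the sized V6–V1 paired test in a single-arm cohort selected for excess weight can show only change

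*Combined protocol and SAP*

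**What the plan says.** PURPOSE OF THE STUDY gives the aim as follows: "The aim of the study is to evaluate the effect of administering a normo/hypocaloric Mediterranean diet regimen on body composition in pediatric children". The same paragraph repeats the causal wording, and also mentions assessing body composition in relation to adherence.

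MATERIALS AND METHODS recruits children who attend the clinic "for first visit or checkup for excess weight between January 1, 2024, and May 30, 2024" and who are overweight or obese by IOTF criteria. The introduction describes those criteria thus: "a state of overweight is defined from the 75th percentile and a state of obesity from the 95th percentile". All receive the dietary pattern after the V1 assessment. Under Follow-up, "Patients will be evaluated at the time of enrollment (V1), after 3 months (V3) and after 6 months (V6) as per clinical practice". No control group, run-in or second pre-diet measurement is described.

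Calculation of sample size uses a V1 mean BMI z-score of 2.81, an SD of 0.9 and "a correlation between the measurements at V6 and V1 of 0.5", and arrives at 70 children for a change of 0.3. STATISTICAL ANALYSIS begins with paired t tests of V6 against V1. Mixed models for Mediterranean diet adherence and time follow, adjusted for V1 measures. EXPECTED RESULTS anticipates improvement at 6 months, once the diet is in place. Regression to the mean is not mentioned.

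**The concern.** The paired test answers whether the cohort's mean changed. The aim asks whether the diet changed it. With no untreated comparison, three other explanations for a change remain open:

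- **Regression to the mean.** Children enter because they attend for, and have, a high BMI. If entry depends partly on a value that is high for that child, the next value is lower on average without treatment.
- **Growth and puberty.** Six months matter at ages 6 to 17, particularly for body-composition measures that are not standardised for age.
- **Season.** V1 between 1 January and 30 May puts V6 between about 1 July and 30 November, so time on the diet and season move together for every child. The documents give neither a direction nor a size for this.

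More children would estimate the change more precisely, but would not show its cause. A significant fall could be reported as an effect of the diet when an untreated group recruited in the same way might also have fallen.

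**Working it through.** **Inputs from the protocol:** V1 mean 2.81, SD 0.9, V1–V6 correlation r = 0.5, target change 0.3 z, n = 70, 80% power, two-sided 0.05.

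**Inputs that are assumptions:** the source mean m, any r other than 0.5, equal SDs at V1 and V6, and the reading of percentiles as standard normal z-scores (75th ≈ 0.67, 95th ≈ 1.645).

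**1. The plan's own figure.** SD of change = 0.9 × √(2 × (1 − 0.5)) = 0.9. Then n = (0.9 × (1.960 + 0.842) / 0.3)² = 70.6, which agrees with the stated 70 within rounding. The sample size therefore belongs to the paired V6–V1 comparison.

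**2. Fall expected with no diet effect.** Regression to the mean = (1 − r) × (2.81 − m). At r = 0.5 this equals 0.3 when 2.81 − m = 0.3 / 0.5 = 0.6, that is, m = 2.21. It is smaller for any higher m.

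| Assumed m | r = 0.5 | r = 0.8 | r = 0.9 | r = 0.95 |
|---|---|---|---|---|
| 1.645 | 0.58 | 0.23 | 0.12 | 0.06 |
| 2.21 | 0.30 | 0.12 | 0.06 | 0.03 |
| 2.5 | 0.16 | 0.06 | 0.03 | 0.02 |

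**3. What the eligibility cut-off alone would produce.** Suppose clinic attenders are normally distributed and only the cut-off selects among them. Fit that distribution so that the children above the cut have mean 2.81 and SD 0.9:

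| Cut-off | Fitted m | Fall at r = 0.5 | Fall at r = 0.9 |
|---|---|---|---|
| z 0.67 (overweight as described) | 2.78 | 0.015 | 0.003 |
| z 1.3 (assumed) | 2.54 | 0.13 | 0.03 |
| z 1.645 (obesity as described) | 1.41 | 0.70 | 0.14 |

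The first row is small because the overweight cut-off lies (2.81 − 0.67) / 0.9 ≈ 2.4 SD below the assumed V1 mean, so it removes about 1% of attenders. The last row is not the eligibility rule, since overweight children may enter. It shows how sensitive the answer is to where selection acts.

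**4. Effect on the paired test.** With n = 70 and SD of change 0.9, a fall of 0.1, 0.2 or 0.3 z due wholly to regression to the mean would be significant with probability of about 15%, 46% or 80% (normal approximation). A higher r shrinks the bias, but it also shrinks the SD of change. At r = 0.9 the SD of change is 0.9 × √0.2 = 0.40, and the false-positive risk falls less than the bias does.

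**The case against.** The strongest reply is that the size is speculative. The source mean is nowhere in the documents, and r = 0.5 is a planning value given without support. The documented overweight cut-off, acting alone, yields almost nothing. This stands. A reader might infer that the planned mean of 2.81 and correlation of 0.5 by themselves imply a large regression to the mean. They do not: without m they imply no figure. Taking m = 0, the general-population mean, is tempting and gives 1.41 z at r = 0.5, but it does not fit the plan's own numbers. A standard normal population cut so that its selected mean is 2.81 needs a cut near z 2.49 and leaves a selected SD of about 0.30, not 0.9.

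A second reply is that V1 is not the plan's only comparator. This stands too. The mixed model contrasts children by adherence, with V1 adjusted for, and a fall common to all children does not by itself create that contrast. But the contrast is observational, and the model's time term has the same before–after limitation as the t test.

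Lastly, the t tests are described only as assessing variation, and the quoted aim concerns body composition, whereas the figures here concern BMI z-score. That softens the point without removing it. The aim is stated causally twice, the paired tests cover all anthropometric measures, and measures correlated with BMI are open to the same bias. The small result for the overweight cut-off also assumes that attendance itself selects nothing, although these children attend because of excess weight.

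**Conclusion.** The mismatch between aim and design is real and does not depend on any assumed number: a causal aim, one treated cohort selected for excess weight, and a sized analysis that measures change from V1. A significant V6–V1 fall would not by itself be evidence of a diet effect, at 70 children or any other number.

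The amount due to regression to the mean is not established. At r = 0.5 it runs from about 0.015 z (overweight cut-off alone), through about 0.13 z (assumed cut at z 1.3), to 0.3 z or more if m is 2.21 or lower. All of these shrink if r is higher. The documents do not support the statement that regression to the mean will produce the 0.3 z target. They only leave that possibility open. The study can proceed, but its stated conclusion should change.

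**What to change.** 1. In PURPOSE OF THE STUDY, EXPECTED RESULTS and the eventual conclusion, word the V6–V1 result as change over 3 and 6 months after the diet was prescribed. State that it is not by itself evidence of a diet effect, and apply the same limit to the time term of the mixed model.
2. Make the already planned mixed-model adherence contrast, adjusted for V1, the basis of any diet-related statement, and report it as an association.

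Optional additions:

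- Print a sensitivity range for regression to the mean beside the V6–V1 estimate, with m and r labelled as assumptions and without the m = 0 case.
- For checkup patients, show earlier BMI z-scores from the chart as a descriptive diagnostic only. They exist for an unknown subset, and selection at V1 also predicts a rise before V1, so they should not be subtracted from the V6–V1 change.

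The two main changes need no new visits or patients: they alter wording and the emphasis on a model already planned. The chart values would need a short extraction. The cost is a weaker headline claim.

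### In one treated group of growing children, V6-V1 change in height, weight, raw BMI or bioimpedance masses in kg mixes normal growth with any diet effect

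*Combined protocol and SAP*

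**What the plan says.** The PURPOSE OF THE STUDY section sets the aim: "we want to evaluate the effect of administration of a normo/hypocaloric Mediterranean diet regimen on pediatric body composition". MATERIALS AND METHODS enrols one group ("Ages between 6 and 17 years old"), gives every child the diet pattern and describes no comparison group.

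The anthropometric list under Follow-up, measured at V1, V3 and V6, mixes two kinds of measure. BMI SDS and the growth percentile are referenced to age and sex. Height, weight, raw BMI and bioimpedance are listed without any scaling. Waist-to-height ratio lies between: it is scaled for height but not for age. No bioimpedance variable or unit is named there; the background says that the technique allows "quantitative and qualitative analysis of body composition by assessing lean mass, fat mass, and body water percentage".

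The STATISTICAL ANALYSIS section then states: "T tests for paired data will initially be used to assess the presence of variation in anthropometric measures between V6 and V1". It does not limit the tests to scaled measures. Mixed models with adherence and time follow, adjusted for V1 values and baseline characteristics, with covariates chosen stepwise. EXPECTED RESULTS anticipates "an improvement in body composition 6 months after the first visit and then the implementation of the dietary pattern". The sample size is set on the z-score: "70 children will be enough to be able to observe a change in BMI z-score of 0.3".

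**The concern.** Children in this age range grow over six months whether or not they follow a diet. With no comparator, the mean V6-V1 change in an unscaled measure is the sum of growth, any diet effect and other time trends, and a paired test cannot separate them. Body composition is the outcome named in the aim, and its measurements come from bioimpedance, for which no growth-adjusted form is stated.

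The direction of the error depends on the measure:

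- **Height, weight, raw BMI and fat mass in kg.** Growth generally pushes these up. For weight and fat, where a reduction is the hoped-for result, the main risk is that a real loss is masked.
- **Lean mass in kg.** Growth also pushes this up, and a rise could be read as the expected improvement.

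The later mixed models help only in part. Their time term still combines growth with diet. Their adherence term is protected from average growth, but stepwise selection does not guarantee that age, sex and Tanner stage stay in the model.

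**Working it through.** **Step 1. The plan's own figure.** From Calculation of sample size: SD 0.9, V1-V6 correlation 0.5, change 0.3, two-sided 0.05, power 80%.

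- SD of change = 0.9 × √(2 × (1 − 0.5)) = 0.9.
- n = ((1.960 + 0.842) × 0.9 / 0.3)² = 70.6. The stated 70 is reproduced by the normal approximation, apart from rounding up to 71.
- Standardised change = 0.3 / 0.9 = 0.333. The noncentral t distribution gives 78.5% power at n = 70.

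**Step 2. The same sensitivity applied to growth.** The paired test responds to the mean change divided by its SD, whatever the cause. At n = 70 it is significant once the observed mean change exceeds 1.995 / √70 = 0.24 SD. A growth-only shift with no diet effect is therefore significant in:

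- 79% of trials at one third of the SD of change;
- 28% of trials at one sixth.

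These are true changes, not type I errors. The documents do not say how large growth is relative to the SD of change in any raw measure.

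**Step 3. Weight (assumed inputs).** BMI held at 27, starting height 1.45 m, SD of weight change 3 to 5 kg. Weight gain = 27 × (h₁² − 1.45²).

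| Growth | Weight gain | Significant gain, SD 5 to 3 kg |
|---|---|---|
| 1 cm | 27 × (1.46² − 1.45²) = 0.79 kg | 25% to 58% |
| 2 cm | 27 × (1.47² − 1.45²) = 1.58 kg | 74% to 99% |

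These are significant gains. Under the same inputs, the chance that growth alone gives a significant weight loss is below 0.1%. Because BMI is held fixed, the table says nothing about raw BMI.

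**Step 4. Bioimpedance masses, if analysed in kg (assumed SD of change 1.5 to 3 kg).**

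- Lean mass: a growth-only gain of 0.5 kg is 0.333 to 0.167 SD, significant in 79% to 28% of trials.
- Fat mass: a true loss of 0.8 kg has 99% to 59% power. If growth adds 0.3 kg, the net loss is 0.8 − 0.3 = 0.5 kg and power falls to 79% to 28%.

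**Step 5. Adherence term with no true effect (simulation, assumed inputs).** V6 was regressed on V1 and adherence, n = 70. The worst case examined had a correlation of −0.4 between adherence and age, growth varying by 0.4 kg per SD of age, and SD of change 1.5 kg.

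| Correlation of V1 value with age | Rejection without age in the model |
|---|---|
| 0 | 14% |
| 0.5 | 11% |
| 0.8 | 6% |

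With age in the model, rejection is about 5% throughout. In the mildest setting (correlation −0.2, 0.2 kg per SD of age, SD 3 kg) it is about 5% even without age.

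**The case against.** The strongest reply is that the quoted sentence is not wrong. It uses the paired tests as a first step, to see whether measures vary, and they are valid for that. Nowhere does the plan say that a change in weight, height or kg mass will be credited to the diet. The purpose section also frames the question in terms of adherence, which the mixed models address, and EXPECTED RESULTS ties the BMI expectation to the scaled measure: "A change in body mass index is expected, based on the BMI z-score". All of this stands. What remains is that the aim speaks of the diet's effect, the expected result is an improvement in body composition, and nothing in the analysis section restricts how V6-V1 change in an unscaled measure is to be read.

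A reader might infer that growth will generally be mistaken for benefit. The documents do not support that. A rise in weight or fat would not be taken as success, and growth alone almost never yields a significant weight loss (Step 3). False credit is realistic mainly for lean mass in kg, and the plan does not say that kg is the unit.

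A reader might also infer that the primary result is compromised. BMI z-score is referenced to age and sex, so average growth does not move it.

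The kg figures rest on assumed inputs, and their ranges are too wide to fix the size of the problem. The effect on the adherence term is modest. It fades where the V1 value tracks age strongly, which is plausible for kg masses across ages 6 to 17.

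**Conclusion.** The concern holds in a limited form. For height, weight, raw BMI and any bioimpedance mass in kg, a V6-V1 change in this single group cannot be attributed to the diet, so these tests do not answer the stated aim. For weight and fat the likely consequence is lost sensitivity; for lean mass in kg it is possible false credit.

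The only size that follows from the protocol's own n is conditional: 79% significance for a growth shift of one third of the SD of change, and 28% for one sixth. The rest depends on assumed growth and SDs. For a null adherence effect, omitting age gives about 5-14% rejection under the assumed inputs, and close to 5-6% when the V1 value tracks age strongly.

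The BMI z-score analysis is not affected by average growth. It is still an uncontrolled before-after comparison, so regression to the mean and other time trends remain.

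**What to change.** 1. **Choose scaled measures for inference.** Name the bioimpedance variables and their units. Base V6-V1 inference first on BMI SDS, then on waist-to-height ratio and on percent fat or height-indexed fat and fat-free mass. Report height, weight, raw BMI and kg masses descriptively.
2. **Keep age, sex and Tanner stage in the planned mixed models**, whatever the stepwise procedure selects.
3. **Word V6-V1 results as within-group change during follow-up.** State as limitations that measures scaled but not age-referenced can still drift with puberty, and that scaling does not remove regression to the mean.

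Adding age at each visit to the model is not a safe alternative. Within a child, age and visit are inseparable, so the result depends on between-child age differences matching within-child growth.

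The cost is SAP wording and a few variables derived from data already collected at V1, V3 and V6; the planned models stay. The downside is fewer significant raw-unit results and a more modest conclusion.

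### Siblings may enter the study, but the analysis clusters only within patient; if siblings enrol and their changes are positively correlated, some standard errors will be slightly too small

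*Combined protocol and SAP*

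**What the plan says.** In the Combined protocol and SAP, Materials and Methods opens recruitment to "All children and adolescents who come to the SCDU of Pediatrics" for excess weight within a five-month window, subject to the listed criteria. The age range is 6 to 17 years. No criterion mentions siblings or limits entry to one child per family.

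The introduction describes the main treatment of obesity as lifestyle change "to achieve a permanent change in habits by involving the entire household". The Follow-up section collects several items that siblings would largely or wholly share: parents' age, parents' smoking, family history and household socioeconomic level. No family identifier is listed; under Data Collection and Analysis each patient simply receives a code.

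The Statistical Analysis section starts with paired t-tests of V6 against V1. It then fits linear mixed models for adherence and time, adjusted for V1 values and baseline characteristics chosen stepwise. On correlation it says only: "A random intercept will be included in the models to account for correlation of within-patient measures". On error control: "All tests will be two-tailed, and the first-type error will be set at 0.05".

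**The concern.** Children of the same family share parents, income and usually meals, so their changes in BMI z-score and body composition may be correlated. A patient-level intercept links the visits of one child but not two children of one family, and the paired t-test links nothing beyond the child's own two measurements.

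If correlated siblings are counted as independent, the 70 children carry less information than 70 unrelated ones. The confidence interval for the V6-V1 change would be too narrow and the two-sided 0.05 level would not quite be held. The same applies to coefficients of covariates that are constant within a household. The sample size has no slack to absorb this. Without a family code at entry, the analyst may be unable either to adjust or to report how many siblings were enrolled.

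**Working it through.** **Inputs from the Calculation of sample size section.** Power 80%, two-sided type I error 0.05, "a corresponding standard deviation of 0.9" for BMI z-score, "a correlation between the measurements at V6 and V1 of 0.5", a change of 0.3 and N = 70.

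**Step 1: the plan's own figure.** Taking equal SDs at V1 and V6, the SD of the change is 0.9 × √(2 × (1 − 0.5)) = 0.9. Under the normal approximation n = (0.9 × (1.960 + 0.842) / 0.3)² = 70.6, which rounds up to 71. The stated 70 is therefore reproduced to within one child, with all children independent. Power at 70 is 79.6% (normal approximation) or 78.5% (noncentral t).

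**Step 2: effect of siblings on the mean change.** Let a share f of the n children be in sibling pairs and let ρ be the correlation between siblings' changes. There are fn/2 pairs, so

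Var(mean) = (1/n²) × [nσ² + 2 × (fn/2) × ρσ²] = (σ²/n) × (1 + fρ).

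The true standard error is √(1 + fρ) times the one the paired t-test reports, to a close approximation. The actual type I error is 2 × [1 − Φ(1.960 / √(1 + fρ))]. The power of a test using the correct standard error is Φ(0.3 / (0.9 × √((1 + fρ)/70)) − 1.960).

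**Step 3: assumed range.** Neither f nor ρ is in the documents. I assume f = 5-30% (about 2 to 10 pairs among 70 children) and ρ = 0.1-0.5.

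| f | ρ | 1 + fρ | True SE / reported SE | Type I error | Power at N = 70 |
|---|---|---|---|---|---|
| 0 | any | 1.000 | 1.000 | 5.0% | 79.6% |
| 5% | 0.1 | 1.005 | 1.002 | 5.1% | 79.4% |
| 10% | 0.3 | 1.030 | 1.015 | 5.4% | 78.5% |
| 20% | 0.5 | 1.100 | 1.049 | 6.2% | 75.8% |
| 30% | 0.5 | 1.150 | 1.072 | 6.8% | 73.9% |

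Simulating 200,000 null data sets of 70 changes per setting gave rejection rates of 5.3% (f 10%, ρ 0.3), 6.2% (20%, 0.5) and 6.7% (30%, 0.5), in line with the formula. An extreme setting of 40% and 0.7 gave 8.3%.

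**Step 4: would a family random intercept repair the time effect?** It is a constant added to both V1 and V6 for everyone in the family, so it drops out of the V6-V1 difference, just as the patient intercept does. In 200 simulated data sets with 14 sibling pairs and ρ = 0.5, the standard error of the time effect was 0.1056 with the patient intercept alone and 0.1056 with a family intercept added. The true SD was about 0.118, which agrees with 0.9 × √((1 + 0.4 × 0.5)/70) = 0.118.

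**Step 5: do family-clustered standard errors repair it?** In simulation, the V6-V1 mean change with family-clustered standard errors held a type I error of 4.9-5.2% in every sibling setting tried. With no siblings it reproduced the paired t-test exactly.

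No calculation was run for household-level covariates or for adherence in the mixed models. For those, only the direction can be argued.

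**The case against.** The strongest reply is that nothing in the documents shows the problem will occur. Siblings are never mentioned, recruitment is five months at one clinic, and no within-family correlation is given. The exclusion of children already on a dietary regimen might also remove a sibling who attends later, though not siblings enrolled together. All of this stands, and it makes the point conditional.

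A reader might infer that siblings share one study diet. The documents do not support this. The sentence about the household is general background on treating obesity, whereas the methods deliver a dietary pattern to the included subjects after clinical examination and bioimpedance. A shared table is plausible, but it is not a study procedure.

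A reader might also infer that the adherence effect is necessarily reported too precisely. That does not follow. KIDMED is scored per child; where siblings differ in adherence, ignoring a positive family correlation can make the standard error too large. Adjustment for V1 values and baseline characteristics may also absorb part of any family correlation.

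Finally, with only a few pairs a family variance is poorly estimated: with 4 to 7 pairs and ρ = 0.3, the within-pair covariance came out zero or negative in 23-29% of simulations. This counts against relying on a family random effect, not against recording the family.

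**Conclusion.** The gap holds as a minor, conditional one. Siblings may enter, and neither the paired t-test nor the patient-only intercept allows for correlation between them. If they enrol and their changes are positively correlated, the standard error of the mean V6-V1 change is understated: the true value is about 0.2-7% larger, with type I error about 5.1-6.8%, under the assumed shares of 5-30% in pairs and correlations of 0.1-0.5. Standard errors of household-level covariates would move in the same direction, by an amount not calculated here. With no siblings there is no effect.

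The flat statement that the plan's standard errors are too small goes beyond the documents, which supply neither of the two quantities it needs. Rates above 8% arise only in a corner (40% in pairs, correlation 0.7) for which the documents give no support.

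**What to change.** - **Data.** Record a coded family number with the patient code at enrolment, and report how many families contribute more than one child.
- **V6-V1 change.** Keep the simple mean change as the estimate and give it family-clustered standard errors with a small-sample correction and degrees of freedom equal to the number of families minus 1. With one child per family this is the paired t-test.
- **Mixed models.** Only if some families contribute more than one child, use family-clustered (empirical) standard errors, or family random effects that include a family-by-time term. A family random intercept alone should not be relied on, because it leaves the V1-to-V6 time effect uncorrected. If no family contributes two children, keep the models as planned, since a family variance could not be separated from the other terms.

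The cost is one extra data column, a small change to the SAS code, and slightly wider intervals if siblings are present.
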